6.9. Concomitant Medications

Concomitant medications, including over-the-counter medications and supplements, taken during the study will be recorded in the eCRF. Start/stop dates and route of administration will be recorded for general concomitant medications. Additional details (e.g., changes in dose, reason for change, reason for addition and termination) will be recorded for certain medications at each visit (i.e., iron and anti-hypertensive medications).

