11. PK sampling will be collected from all subjects randomized to the daprodustat arm at 1 of these 3 visits, Details in Section 7.5.
12. Informed consent for optional genetic research should be obtained before collecting a sample. To minimize potential study bias, the genetic sample should be collected on Day 1.
13. Subjects who are unable to or require assistance to read must not complete the questionnaires.
14. To be completed if available (e.g., translations may be not available in time in all countries).
15. Only SAEs assessed as related to study participation or a GSK product are collected during screening period
16. In circumstances where the new dose of randomized treatment cannot be dispensed on the day of the study visit, the new dose of randomized treatment can be dispensed at next HD treatment. For visits after Day 1, prior randomized treatment should be continued unless on dose hold, Hgb \geq 12 g/dL. Compliance is deferred until randomized treatment is returned
17. For Argentina, ONLY: pregnancy testing will be performed every 4 weeks for FRP as required by local law
18. Biomarker samples will be stored for future analyses for all subjects, except if not permitted by IRB/EC or refused by subject.
19. Informed consent will be obtained prior to any study procedures.

Table 7 TIME AND EVENTS TABLE FOR SUBJECTS THAT PERMANENTLY DISCONTINUE RANDOMIZED TREATMENT

Protocol Activity	Early Treatment Discontinuation Visit (within 2 weeks of the last dose of randomized treatment)	Day 1 – Week 52 (every 12 weeks \pm 2 weeks)	Unscheduled	Follow-up (4 weeks post-study termination \pm 1 week)
Dialysis: In-clinic assessments done pre-dialysis.				
IRT SYSTEM	X			
SBP/DBP ¹ , HR ¹	X (triplicate)	X	X	X
Iron therapy, transfusions ²	X			
Serum pregnancy test (FRP only)	X			
HemoCue Hgb	X	X	X	
Hematology	Hgb only	X		X
Clinical chemistry	X			
Ferritin, serum iron, UIBC, hepcidin, lipids	X			
Hospitalization ² / kidney transplant ²	X	X	X	X
Non-serious AEs, AEs of Special Interest, SAEs, clinical events	X	X	X	X
Review concomitant medications	X	X	X	X
Healthcare resource utilization (subject reporting)	X			
CKD Anemia Symptoms Questionnaire (CKD-AQ) questionnaire, PGI-S, PGI-C ³	X			
SF-36 ³ , EQ-5D-5L ³	X			

1. See Section 7.4.8 for details.

2. Record in eCRF, if applicable

3. Subjects who are unable to or require assistance to read must not complete the questionnaires.

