9.4.2. Secondary Analyses

9.4.2.1. Principal Secondary Efficacy Analyses

Conditional on the primary endpoint achieving non-inferiority at the one-sided 2.5% level, statistical testing will progress to the principal secondary endpoint with a focus on superiority using a one-sided 2.5% significance level.

For the average monthly IV iron dose up to Week 52 endpoint: IV iron use for all subjects will be recorded in the eCRF and the average monthly IV iron dose up to week 52 while on treatment will be calculated. An ANCOVA model will be used to compare the difference in this average monthly IV iron dose per subject between arms, including factors for baseline dose, treatment and the randomization stratification factors.

Additional secondary/exploratory endpoints are listed in [Appendix 2](#). All analyses of secondary endpoints are of exploratory nature, summary statistical and nominal one-sided -p values will be used to describe the results and for any treatment comparisons.

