Model Results Interpretation

 • See Section 10.11.1.

CONFIDENTIAL

201410

Supportive Statistical Analyses
Average monthly IV iron dose (mg)/subject to Week 52 using on and off treatment IV iron records, regardless of transfusion

 • The summaries and analysis described above for the principal secondary average monthly IV iron dose/subject to Week 52 will be repeated using all available IV iron records during the Day 1 – Week 52 visits, regardless of whether or not a subject was on treatment or transfusion • The average monthly IV iron dose (mg)/subject to Week 52 for this analysis will be determined by calculating the total IV iron dose per subject from Day 1 to the earliest of (Week 52 visit date, study completion/withdrawal date) and dividing by (earliest of the (Week 52 visit date, study completion/withdrawal date) – Randomization date + 1 day)/30.4375 days.
Subgroup Analysis

 • Subgroup analysis details are discussed in Section 10.10.1.

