10.6.3.2. Iron Endpoints

Iron Endpoints
Iron Medications

 During the study, subjects may be receiving iron in multiple routes, including: 
 IV iron Oral iron Other iron (including intramuscular, subcutaneous, and hemodialysis/dialysate) Note: The iron route categories above will be determined using the route on the Prior/Concomitant Medication – Iron Therapy record. In addition, ferric citrate records recorded on the Prior/Concomitant Medication – Metabolic Bone Disease Therapy eCRF form will also be summarized as oral iron use.
Baseline Iron Use

 The number and percentage of subjects in the following iron use categories at baseline will be summarized: 
 IV iron use only Oral iron use only Other iron use only IV and oral iron use only IV and other iron use only Oral and other iron use only

CONFIDENTIAL

201410

Iron Endpoints	

 ○ IV, oral, and other iron use ○ No iron use ● When determining baseline iron use, the gap factors mentioned below in the IV iron standardization algorithm will be applied to the end date for each iron record, and the baseline period of 10 weeks before the Randomization date until the day before the Randomization date will also be used. 	
Standardized IV Iron Dose (mg/week) to Determine Iron Management Action	

 ● In order to compare between IV iron records, to determine the action taken with IV iron therapy in the 8 weeks following the date the IV management threshold was met, the dose of IV iron in each associated record will be standardized in terms of mg/month. ● IV iron therapy concomitant medication records that occur or are ongoing during the 8 weeks following the date the IV management threshold was met (inclusive), will be selected and ordered by start and end date. 
 ○ If there is a record has a start date on the date the IV management threshold was met, and a prior record has an end date on the day before the IV management threshold was met, this prior record will be selected and considered as well. ● The standardization will be carried out with the following formula: 
 ○ Standardized IV iron dose (mg/week) = IV iron drug dose (mg) * frequency 	
Note: Frequency defined as follows:	
Frequency (from eCRF)	Frequency (for standardization formula)

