
 ● In order to calculate the average monthly IV iron dose from Randomization to Week 52, the dose of IV iron will be standardized to obtain a continuous single unit IV iron dose in terms of mg/month for the period from the Randomization date to the Week 52 visit date while the subject is on treatment and before their first RBC or whole blood transfusion. 
 ○ Note: Subjects who are randomized but never treated will not have a value for average monthly IV iron from Randomization to Week 52. ● IV iron therapy concomitant medication records that occur or are ongoing during the period from the subject's Randomization date – 10 weeks to the Week 52 visit date will be selected and ordered by start date and end date. ● The standardization will be carried out with the following formula: 
 ○ Standardized IV iron dose (mg/week) = IV iron drug dose (mg) * frequency 		
Note: Frequency and Gap Factors defined as follows:		
Frequency (from eCRF)	Frequency (for standardization formula)	Gap Factor
2 times per week	2	2.5 days
3 times per week	3	1.33 days
4 times per week	4	0.75 day
5 times per week	5	0.4 day
BID	14	0 days
Once daily	7	0 days
One time dose	1	n/a
Every 12 Hours	14	0 days
Every 2 weeks	0.5	13 days
Every 4 weeks	0.25	27 days
Once a month	0.23	29 days
Once a week	1	6 days
TID	21	0 days

 ● If the frequency of the record is not 'one time dose', then duration is calculated as follows: 
 ○ If the concomitant medication record start date > earliest of (treatment stop date +1 and Week 52 visit date), the duration of the record is 0. ○ If the concomitant medication record end date + gap factor < Randomization date, the duration of the record is 0. ○ If the concomitant medication record end date + gap factor \geq Randomization date or the record is ongoing, the duration of the record will be calculated as Stop Date – Start Date +1 day where: 
 ▪ Start date will be the latest of (concomitant medication record start date, randomization date, treatment start date). 		

CONFIDENTIAL

201410

Iron Endpoints		

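### Table 7 drops the iron row after the discontinuation visit, at odds with Protocol 6.9 and 9.4.2.1, so the on-and-off-treatment IV iron analysis may count unascertained time as zero iron

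*Protocol*

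**What the plan says.** **Visit schedules.** Table 7 in Protocol 7.1 covers subjects who have permanently stopped randomized treatment. Its row "Iron therapy, transfusions" is marked at the Early Treatment Discontinuation visit and is blank at the 12-weekly, unscheduled and Follow-up columns. SAP 10.2.1.2 reproduces the same pattern. In the same table, "Review concomitant medications" is marked in all four columns. Table 6, for subjects on treatment, marks the iron row at every scheduled visit from Day 1 and at Follow-up, but not at unscheduled visits.

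**Recording rules.** Protocol 6.9 says that additional details "will be recorded for certain medications at each visit (i.e., iron and anti-hypertensive medications"), with no on-treatment limit. Protocol 9.4.2.1 says "IV iron use for all subjects will be recorded in the eCRF".

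**Data source.** SAP 10.6.3.2 takes iron from concomitant medication data: "The iron route categories above will be determined using the route on the Prior/Concomitant Medication – Iron Therapy record". The dose to Week 52 is built from "IV iron therapy concomitant medication records that occur or are ongoing during the period" of interest.

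**Analyses.** In SAP 8.1.1.2 the principal secondary analysis stops at the earliest of the Week 52 visit, the first transfusion, and the day after treatment stop. The supportive analysis is repeated "using all available IV iron records during the Day 1 – Week 52 visits", regardless of treatment or transfusion. Its divisor is built from "earliest of the (Week 52 visit date, study completion/withdrawal date) – Randomization date + 1 day)/30.4375 days".

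**The concern.** The supportive analysis keeps the clock running after treatment stops, but the schedule for that period no longer shows the row dedicated to iron. On treatment, the iron row and the concomitant medication row appear side by side, so a site may treat them as separate instructions and read the later blanks as deliberate. Protocol 6.10, which limits the iron management criteria to subjects receiving randomized treatment, could encourage that reading.

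The SAP has no rule for off-treatment time in which iron was not ascertained. Such time adds days to the divisor and nothing to the dose. Subjects followed only by alternative contact are also exposed, because Protocol 5.5.1 counts them as remaining in the study.

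Apart from subgroups, this is the only supportive analysis planned for the principal secondary endpoint. If capture is incomplete, its result would partly reflect how long subjects stayed on treatment.

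**Working it through.** **1. The plan's own figure.** The documents give no planning figure for IV iron. The only relevant input is the early stopping assumption in Protocol 9.2.1: up to about 30% before Week 28. It reproduces the stated precision for the hemoglobin endpoint: 150 × 0.70 = 105 per arm, and t(0.975, 208 df) × 1.5 × √(2/105) = 1.971 × 0.2070 = 0.408 g/dL, as stated.

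**2. One subject, nothing recorded after the discontinuation visit.** Assume a constant true iron rate and a discontinuation visit 2 weeks after the last dose, the latest allowed. Recorded share of true monthly dose = (stop week + 2)/52:
- stop at Week 4: 6/52 = 11.5%
- stop at Week 16: 18/52 = 34.6%
- stop at Week 28: 30/52 = 57.7%
- stop at Week 40: 42/52 = 80.8%

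**3. Arm mean under a constant stopping hazard.** Assume 30% stopped by Week 28, no off-treatment capture, and all subjects in the study to Week 52.
- Hazard = −ln(0.70)/(28/52) = 0.662 per 52 weeks
- Stopped by Week 52 = 1 − exp(−0.662) = 0.484
- Mean on-treatment share of the 52 weeks = 0.484/0.662 = 0.731
- Dilution = 1 − 0.731 = about 27%

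**4. Unequal stopping.** Add two assumptions: 25% versus 35% stopped by Week 28, and a true 90 mg/month in both arms. The on-treatment shares become 0.775 and 0.688. The apparent means are about 69.7 and 61.9 mg/month, a spurious difference of about 8 mg/month.

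**5. Sensitivity to the stopping pattern.** Suppose instead that a fraction d stops at a single week s, so that arm mean/truth = (1 − d) + d(s + 2)/52.
- d = 30%: 73.5% (Week 4), 79.2% (Week 14), 87.3% (Week 28)
- Over d = 20% to 40% and these weeks: from 0.60 + 0.40 × 6/52 = 64.6% to 0.80 + 0.20 × 30/52 = 91.5%
- 20% versus 30% stopping at Week 14: 0.8615 − 0.7923 = 6.9% of the true mean

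The 27% therefore belongs to its stated assumptions; other assumed patterns with zero capture give 8.5% to 35.4%.

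**6. The other end.** If concomitant medication review captures all off-treatment iron, the recorded share is 100% and the bias is zero.

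**7. Direction.** SAP 10.6.3.2 lets ongoing records accrue to the end of the analysis window. If that rule is carried over with the supportive end date in place of treatment stop + 1 day, an iron record left open at the discontinuation visit keeps adding dose. The error can then be upward.

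**The case against.** The strongest reply is that off-treatment capture is already provided for. Protocol 6.9 and 9.4.2.1 require it, Table 7 keeps the concomitant medication row active at every column, and the SAP builds the endpoint from those medication records. The blank cells also have an innocent explanation: once the iron management criteria no longer apply, iron is an ordinary concomitant medication. This stands as far as it goes. A reader might infer from Table 7 that off-treatment iron is not collected at all, and the documents do not support that. They show an ambiguity that could lead some sites to stop asking.

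A reader might also infer that the formally tested endpoint is biased. It is not: its window closes at treatment stop + 1 day. The exposed analysis carries no alpha.

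The size is open to challenge too. The supportive divisor ends at study completion or withdrawal, and death counts as completion (SAP 10.6.1), so subjects who die on treatment or withdraw on stopping add little off-treatment time. The constant-hazard figure also ignores recording at the discontinuation visit. Both points reduce it.

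The reply does not remove the inconsistency between Table 7 and Protocol 6.9 and 9.4.2.1, or the lack of an SAP rule for time without ascertainment.

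**Conclusion.** The point holds as an inconsistency in the visit schedule plus a missing SAP rule. It affects the supportive on-and-off-treatment analysis and leaves the principal secondary test, the sample size and the power unchanged.

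The bias lies between zero, with full capture through medication review, and about 27% dilution, with no off-treatment capture, a constant stopping hazard and a constant iron rate. The difference of about 8 mg/month additionally needs 25% versus 35% stopping and 90 mg/month in both arms. None of these assumptions comes from the documents except the 30% stopping by Week 28, so the figures should not be read as expected effects. Nor do the documents support the inference that the arm with more early stopping must appear to use less iron, because open records can push the other way.

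The correction is worth making because it is cheap and protects the only non-subgroup supportive analysis of this endpoint.

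**What to change.** **Schedule.** In Protocol Table 7 and SAP 10.2.1.2, mark the iron and transfusion row at the 12-weekly and Follow-up columns. This matches Table 6 at scheduled visits and agrees with Protocol 6.9 and 9.4.2.1. The Follow-up mark picks up iron given between the last 12-weekly visit and Week 52. Leave the unscheduled column blank, as Table 6 does.

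**SAP 8.1.1.2.** End both numerator and denominator of the supportive analysis at the earliest of the Week 52 visit, study completion/withdrawal, and the last contact at which concomitant medications, including iron, were reviewed. Count reviewed intervals with no iron record as true zeros. Do not truncate merely because no iron was entered: iron is entered only if applicable, so a missing record may mean none was given, and cutting that time would bias use upward. The same end date stops a record left open from accruing past the last review.

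**Cost.** Extra marks in one row at visits that already take place, slightly more eCRF entry, and one SAP sentence.

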7.2. Screening and Critical Baseline Assessments

Before any study-specific procedure is performed, valid informed consent must be obtained.

Demography and medical history will be assessed at the initial screening visit.

Randomization requires an Hgb level within the specified range (Section 5.1) and levels of serum ferritin or TSAT as outlined in Section 5.2.

Full details of screening and baseline (Day 1) assessments are provided in the Time and Events Table (Table 6).

7.3. Efficacy

Planned time points for all Hgb efficacy assessments are listed in the Time and Events Table (Table 6).

GSK will supply a point-of-care Hgb analyzer (i.e., HemoCue) to each site for rapid measurement of Hgb.

Blood samples (not fingersticks) for measurement of Hgb via HemoCue, and also by the central laboratory will be collected as specified in the Time and Events Table (Table 6).

7.4. Safety

Safety endpoints will include monitoring of deaths, AEs, SAEs, other CV events, AEs of special interest, AEs leading to discontinuation of randomized treatment, and laboratory parameters, blood pressure and heart rate (HR).

Planned time points for all safety assessments are listed in the Time and Events Table (Table 6). Unscheduled visits will occur as medically necessary. Detailed procedures for obtaining each assessment are provided in the SRM.

7.4.1. Events Referred to the Clinical Event Committee (CEC)

Investigators should refer any event suspected to be one of the events below to the CEC. The CEC will review and adjudicate the following clinical events. See CEC Site Manual for full scope of reporting requirements.

- All-cause mortality (CV and non-CV mortality)
- Non-fatal myocardial infarction (MI)
- Non-fatal stroke
- Hospitalization for heart failure
- Thromboembolic events (vascular access thrombosis, symptomatic deep vein thrombosis, symptomatic pulmonary embolism)

Events referred to the CEC will be subjected to blinded adjudication using pre-specified diagnostic criteria.

When the investigator-reported event and the CEC assessment of the event differ, the CEC's decision will be considered final. The detailed descriptions of the endpoint definitions used for adjudication are contained within the CEC Charter (available on request).

Source documentation required to support the adjudication of the events is described in the CEC Site Manual.

7.4.2. Other CV Events

GSK has identified other CV events of interest for all clinical studies. Investigators will be required to fill out the specific CV event page of the eCRF for the following categories of events:

- Arrhythmias
- Pulmonary hypertension*
- Valvulopathy
- Revascularization

(* Pulmonary hypertension is also an AE of special interest for the current study, see Section 7.4.4 for details.)

7.4.3. Adverse Events (AE) and Serious Adverse Events (SAEs)

The definitions of an AE and SAE can be found in [Appendix 8](#).

The investigator or their designees are responsible for detecting, documenting and reporting events that meet the definition of an AE or SAE.

7.4.3.1. Time period and Frequency for collecting AE and SAE information

- Any SAE assessed as related to study participation (e.g., protocol-mandated procedures, invasive tests, or change in existing therapy) or related to a GSK product will be recorded from the time subject consents to participate in the study up to and including any follow-up contact.
- AEs will be collected from the start of randomized treatment until the Follow-up visit, at the timepoints specified in the Time and Events Table ([Table 6](#)).
- Medical occurrences that begin prior to the start of randomized treatment but after obtaining informed consent will be recorded on the Medical History/Current Medical Conditions section of the eCRF.
- All SAEs will be recorded and reported to PPD within 24 hours, as indicated in [Appendix 8](#).
- Investigators are not obligated to actively seek AEs or SAEs in former study subjects. However, if the investigator learns of any SAE, including a death, at any time after a subject has been discharged from the study, and he/she considers the event reasonably related to the randomized treatment or study participation, the investigator must promptly notify PPD.

NOTE: The method of recording, evaluating and assessing causality of AEs and SAEs plus procedures for completing and transmitting SAE reports to PPD are provided in [Appendix 8](#).

7.4.3.2. Method of Detecting AEs and SAEs

Care will be taken not to introduce bias when detecting AEs and/or SAEs. Open-ended and non-leading verbal questioning of the subject is the preferred method to inquire about AE occurrence. Appropriate questions include:

- “How are you feeling?”
- “Have you had any (other) medical problems since your last visit/contact?”
- “Have you taken any new medicines, other than those provided in this study, since your last visit/contact?”

7.4.3.3. Follow-up of AEs and SAEs

After the initial AE/SAE report, the investigator is required to proactively follow each subject at subsequent visits/contacts. All SAEs, and non-serious AEs of special interest (as defined in Section 7.4.4) will be followed until resolution, until the condition stabilizes, until the event is otherwise explained, or until the subject is lost to follow-up (as defined in Section 5.6.2). Further information on follow-up procedures is given in [Appendix 8](#).

7.4.3.4. Regulatory Reporting Requirements for SAEs

Prompt notification by the investigator to PPD of SAEs related to randomized treatment is essential so that legal obligations and ethical responsibilities towards the safety of subjects and the safety of a product under clinical investigation are met.

GSK has a legal responsibility to notify both the local regulatory authority and other regulatory agencies about the safety of a product under clinical investigation. GSK will comply with country specific regulatory requirements relating to safety reporting to the regulatory authority, Institutional Review Board (IRB)/Independent Ethics Committee (IEC) and investigators.

Investigator safety reports are prepared for suspected unexpected serious adverse reactions according to local regulatory requirements and GSK policy and are forwarded to investigators as necessary.

An investigator who receives an investigator safety report describing a SAE(s) or other specific safety information (e.g., summary or listing of SAEs) from GSK will file it with the IB and will notify the IRB/IEC, if appropriate according to local requirements.

